9.3 Treatments

Exposure to investigational study medication is defined as the number of days spent on study drug divided by 365.25 days. In this double-dummy design all patient will receive capsules (active or placebo) and injections (active or placebo) to maintain the blind. For the calculation of exposure to study medication only the active drug will be considered. Intermediate treatment interruptions will be subtracted from drug exposure.

Exposure to investigational study medication will be summarized by treatment with number and percentage of patients by time category, and with summary statistics of the number of patient years of exposure. Number of patient years will be summarized by age and gender, by gender and weight, as well as by race.

Time-at-risk is defined as the number of days spent in the study, from first dose to the last dose of study medication, plus the safety data cut-off of 100 days. Intermediate treatment interruptions will be included in time-at-risk calculations. Time-at-risk corresponds to the time window used for adverse event reporting and can serve as a denominator to safety (e.g. in exposure-adjusted incidence rates). Time-at-risk will be summarized in a similar way to exposure to investigational study medication.

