There will be three reports resulting from this SAP: (1) The clinical study report (CSR) of the G2301 study, (2) the CSR of the G2302 study, and (3) a combined report containing side-by-side presentation of demography and baseline characteristics between the two ASCLEPIOS studies, and key-secondary analyses on the pooled data from the two studies as defined in the clinical study protocols. Specifically the combined report will contain the analysis results concerning disability worsening and disability improvement from the combined data of the two studies. These three reports will be generated twice and referred to as 1) registration CSR and 2) final CSR. The registration CSR will be completed at the time of submission for new drug application. The final CSR will be completed after the final database lock.

This document is consistent with the current study protocols (version 02).

The analyses that will be performed for the blinded interim data reviews are out of the scope in this SAP and will be documented in a separate analysis plan. [REDACTED]

[REDACTED] These analyses will be documented in separate analysis plans or modeling reports and are out of scope for the present SAP.

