- 2) Across the two studies, sufficient 3mCDW events have been observed to provide 90% power for the key secondary 3mCDW endpoint.
- 3) Across the two studies, sufficient 6-month confirmed disability worsening (6mCDW) events have been observed to provide 80% power for the key secondary 6mCDW endpoint.

Details of the statistical analysis plan with respect to blinded data reviews are provided in the [BSSR SAP](#).

The core study consists of three epochs: **Screening epoch** (including baseline), **Treatment epoch** (double-blind) and the post-treatment **Safety Follow up epoch** ([Figure 1-1](#)). Patients who complete the double-blind Treatment epoch (on study drug) may be eligible to enter an open-label ofatumumab Extension study that is planned (under a separate protocol).

All patients will have an EOS visit at the end of the Treatment epoch. Patients who prematurely discontinue double-blind study medication and agree to continue to follow the assessment schedule of the Treatment epoch (recommended) will have their end of treatment assessments (EOT) at the time of study medication discontinuation.

Patients who complete the Treatment epoch (on study drug), but do not enter the Extension study will be followed up for safety in the post-treatment Safety Follow-up (Safety FU) for a minimum of 9 months (or longer if indicated). The duration of the Safety FU epoch for an individual patient will depend on how long the patient has been off study drug at the time he/she enters the Safety FU epoch. For example, a patient who completed the Treatment epoch on study drug and had EOS (and will not enter the extension study), will be followed for at least 9 months in the Safety FU epoch. However, a patient who discontinued study drug earlier and had 4 months of follow up after study drug discontinuation in the Treatment epoch may only need to be followed for an additional 5 months in the Safety FU epoch (for a total of 9 months). Continued follow up beyond 9 months will be required for patients who have not repleted their B cells (to LLN or baseline values) or in whom teriflunomide plasma levels are still above 0.02 mg/L at 9 months, unless they have already started treatment with another MS disease modifying treatment (DMT).

Figure 1-1 Study design

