2.1 Data analysis general information

Novartis statistical and programming team will be performing the CSR analysis as planned in this document unless otherwise specified. The Statistical Analysis System (SAS) 9.4 and/or R 15.2.1 or higher versions will be used.

Statistical safety analyses for the independent Data Monitoring Committee (DMC) will be conducted by a CRO. The process is described in the DMC charter.

Unless otherwise stated, summary tables/figures/listings will be on all patients in the respective analysis sets. Categorical data will be presented as frequencies and percentages. For continuous data, mean, standard deviations, median, 25th and 75th percentiles (optional), minimum and maximum will be presented.

The registration CSR analysis cut-off date will depend on the EOS date. All data up to this date will be included in the registration CSR. A complete analysis of the post-treatment safety follow-up will be provided in the final CSR when all patients have completed Safety FU epoch.

For efficacy analyses on the full-analysis set (FAS), all available data until the end of treatment epoch date (i.e., excluding the data collected in the safety follow-up epoch) will be considered and no other cut-offs will be applied.

For efficacy analyses on the per-protocol set (PPS), only on-treatment (as defined in [Section 2.1.1](#)) data will be considered, that is, for patients randomized to receive ofatumumab, data obtained 30 days after the last injection date will be excluded from the analyses; for patients

randomized to receive teriflunomide, data obtained after the last dose date of randomized study medication will be excluded from the analyses.

For safety analyses on the safety set, only data up to and including the safety cutoff of 100 days (5 x 20 days takes the long half-life of the comparator-drug into account) after last administration of study drug will be considered. Therefore, observations obtained more than 100 days after last administration of study drug will be excluded from the analyses. Nevertheless, all serious adverse events (SAE) and all deaths, regardless of the safety cut-off will be summarized.

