End of treatment epoch date	This date is the date of discontinuation/study phase completion as recorded in the Study Phase Completion CRF page.
Last assessment on drug	It is the last assessment with non-missing value taken before or on the date of last administration of study drug. No visit windows will be needed for the identification of the last assessment on drug evaluation.

Table 2-2 Definition of time in key analyses

Time in study (ARR)	Time in study for ARR will be calculated as (end of treatment epoch date – first dose date+1)/365.25. The time in study by patient will be used as an offset variable to adjust for the various length patients have been observed and at risk of a confirmed MS relapse in the study.
Time from screening scan (MRI: key secondary analysis related)	T2 lesions: The time from screening scan will be calculated as (date of last scheduled MRI scan with a non-missing value for the number of new or enlarging T2 lesions during the treatment epoch – date of screening scan +1)/365.25. Brain volume change: Time of MRI assessment from screening scan will be calculated as (date of the scheduled MRI scan – date the screening scan +1)/365.25.

Time at risk for AE	Time at risk for AE is defined as the number of days spent in the study, from first to last administration of study drug, plus the safety data cut-off of 100 days. Time at risk for AE will be used for tables reporting AEs (including both SAE and non-SAE). If the corresponding last day of time at risk for AE is after the analysis cut-off date, then it will be truncated by the analysis cut-off date as defined in Section 2.1 .
Time at risk for SAE	Time at risk for SAE is defined as the number of days spent in the study from the day of first administration of study drug to the end of study date (including safety follow up epoch). Time at risk for SAE will be used only for tables reporting SAEs. If a patient is still in safety follow up epoch at the time of reporting, time at risk for SAE is the number of days from the day of first administration of study drug to the analysis cut-off date as defined in Section 2.1 .

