- **Time at risk for AE** is defined as the number of days spent in the study, from first to last administration of study drug, plus the safety data cut-off of 100 days. Time at risk for AE will be used for tables reporting AEs (including both SAE and non-SAE). If the corresponding last day of time at risk for AE is after the analysis cut-off date, then it will be truncated by the analysis cut-off date as defined in [Section 2.1](#).
- **Time at risk for SAE** is defined as the number of days spent in the study from the day of first administration of study drug to the end of study date (including safety follow up epoch). Time at risk for SAE will be used only for tables reporting SAEs. If a patient is still in safety follow up epoch at the time of reporting, time at risk for SAE is the number of days from the day of first administration of study drug to the analysis cut-off date as defined in [Section 2.1](#).

Time at risk for AE and time at risk for SAE will be summarized in a similar way to duration of exposure to study drug.

Compliance to the study drug administration schedule will be calculated as duration of exposure to study drug in (days)/duration of on-treatment period (as defined in [Section 2.1.1](#)) in (days) $\times 100\%$. This rule means that compliance will be measured during the time interval the patient took study medication: premature discontinuation from study drug will not be considered non-compliance. Compliance to study drug administration will be summarized descriptively on SAF by treatment group. In addition, compliance will be summarized with cumulative number and percentage of patients in each compliance category (*i.e.*, $\geq 20\%$, $\geq 30\%$, $\geq 40\%$, $\geq 50\%$, $\geq 60\%$, $\geq 70\%$, $\geq 80\%$, $\geq 90\%$, $\geq 95\%$, $\geq 98\%$, $=100\%$).

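### AE time at risk can run past the end of observation for patients who leave the core study within 100 days of the last dose, so exposure-adjusted AE rates are understated

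*SAP*

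**What the plan says.** - **AE clock.** SAP 2.4.1 and Table 2-2 count AE time at risk "from first to last administration of study drug, plus the safety data cut-off of 100 days". If that end date falls after the data cut, "it will be truncated by the analysis cut-off date as defined in" SAP 2.1. No other truncation is named. Protocol 9.3 has the same rule, "from first dose to the last dose of study medication, plus the safety data cut-off of 100 days", with no truncation at all.
- **Cut-off and reports.** SAP 2.1: "The registration CSR analysis cut-off date will depend on the EOS date". SAP Introduction: "These three reports will be generated twice and referred to as 1) registration CSR and 2) final CSR". No cut-off date is given for the final CSR. SAP 2.1 says only that it follows completion of Safety Follow-up by all patients.
- **SAE clock.** In the same section, SAE time at risk runs "from the day of first administration of study drug to the end of study date (including safety follow up epoch"), so it stops with the patient's own participation.
- **Use in the rate.** Under SAP 5.7.2 a patient with the event contributes time to first onset, and a patient without it contributes the 2.4.1 time at risk. The same section describes event-free patients as censored when their observation ends.
- **Who leaves observation.** Patients who complete on drug "may be eligible to enter an open-label ofatumumab Extension study", which runs under a separate protocol. Protocol 5.6.3 allows no further assessments after consent is withdrawn.

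**The concern.** The numerator and denominator do not cover the same period. SAP 2.8.1 counts treatment-emergent AEs up to 100 days after the last dose, but such an AE can be recorded only while the patient is still in the core study. A patient who dies, withdraws consent, is lost to contact or enters the extension soon after the last dose still adds up to 100 days to the denominator and cannot add an event to the numerator. The error runs one way: the denominator can only be too long, so the rate can only be too low. For a teriflunomide patient who rolls over, the credited days may even be spent on open-label ofatumumab.

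SAP 2.8.1 plans these rates because follow-up is flexible, and calls them suitable for constant-risk events such as infection or cancer. SAP 2.8.1.1 uses them again for AEs of special interest. For such events the absolute rate is what a reader will quote.

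**Working it through.** The documents state no AE rate or person-time figure that depends on this rule, so there is no planned figure to reproduce. The 100 days is 5 × 20 = 100, which checks.

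**Inputs from the documents**
- Estimator: rate = D/T (SAP 5.7.2).
- Follow-up of 1.5 years = 547.9 days (Protocol 9.8.1).
- Accrual of 500 patients in 6 months, then 1500 per year; 20% dropout over 2 years; study duration 2.5 to 3 years (Protocol 9.8.2).
- Maximum of 30 months on treatment (Protocol 3.1).

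**Assumptions, not in the documents**
- The share f of patients unobserved during the 100 days.
- Extension uptake.
- The share of dropouts with no AE follow-up after the last dose.
- The exact cut-off dates.

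**Rare events, no cut-off truncation.** The SAP denominator per patient is 547.9 + 100 = 647.9 days. The observed denominator is 547.9 + (1 − f) × 100. The understatement is therefore f × 100/647.9:

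| f | Understatement |
|---|---|
| 5% | 0.8% |
| 10% | 1.5% |
| 20% | 3.1% |
| 50% | 7.7% |
| 80% | 12.4% |
| 100% | 15.4% |

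**Common events.** Patients with the event contribute only time to onset, so the bias shrinks. At true rates of 0.1, 0.5 and 1.0 per year it is 14.5%, 10.9% and 7.3% with everyone unobserved, and 2.9%, 2.2% and 1.5% with 20% unobserved.

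**Effect of the cut-off (simulation).** 1800 patients were accrued as above with exponential dropout, and EOS was set at 2.5 or 3 years. The 30-month cap was taken as 840 or 913 days. Assumed: 80–100% of completers enter the extension, and 50–100% of dropouts have no AE follow-up after the last dose.

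| EOS | Registration CSR, cut-off = EOS | Final CSR, cut-off = EOS + 1 year |
|---|---|---|
| 2.5 years | 1.4–3.3% | 11.0–14.8% |
| 3 years | 3.1–6.3% | 9.1–12.7% |

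The registration figure is larger with the later EOS because more patients reach 30 months before the cut-off, so their 100 days are not trimmed.

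**Rate ratio between arms**
- 10% versus 20% unobserved: (637.9/647.9)/(627.9/647.9) = 1.016.
- 15% versus 30% unobserved: 1.024.
- All patients enter the extension, and the last active injection falls 14 days before the EOS visit (assumed) while the last capsule is at that visit: (547.9/633.9)/(547.9/647.9) = 1.022.

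**The case against.** The strongest reply is that the SAP already carries the limiting principle. Its definition starts from days in the study, SAP 2.4.1 ties time at risk to the AE reporting period, and SAP 5.7.2 speaks of censoring when observation ends. On that view only the wording is loose. This does not settle the matter: after referring to days in the study, the definition adds 100 days and names a single truncation, and a programmer following it would count the unobserved days.

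Other parts of the reply stand:
- The cut-off truncation is real. For patients on drug at EOS who then roll over, an EOS-linked registration cut-off removes most of the excess.
- Completers who do not roll over enter Safety Follow-up for at least 9 months. Early discontinuers are asked to stay in the Treatment epoch or enter Safety Follow-up (Protocol 3.1). AEs are collected there, so their 100 days are valid person-time.
- The documents give no figure for extension uptake, or for how often patients in this trial will die, withdraw consent or be lost within the window.
- Safety rests primarily on AE frequency, and no confirmatory test uses these rates.

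The final-CSR cut-off is not stated, so its effect there is inferred. The inference is reasonable: that report follows completion of Safety Follow-up, which lasts at least 9 months for completers who enter it at EOS. A cut-off at that point lies beyond 100 days after EOS and would no longer trim the excess.

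**Conclusion.** The rule as written counts unobserved person-time and understates exposure-adjusted AE rates. It conflicts with the censoring principle in SAP 5.7.2 and with the way the neighbouring SAE clock is built. The direction is certain. The size depends on how many patients leave within 100 days of the last dose and on the cut-off: low single digits up to about 6% in the registration CSR, and about 9–15% in the final CSR, both under the assumed high extension uptake. Crude incidences, odds ratios and SAE-only tables are not affected.

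A reader might infer more than this:
- *That every patient is given 100 unobserved days and rates are 12–21% too low.* The expression 100/(365.25T + 100) does give 21.5%, 15.4% and 12.0% at 1, 1.5 and 2 years, but it is a ceiling. It needs every patient unobserved, rare events and no cut-off truncation. The documents provide for the truncation and for Safety Follow-up.
- *That the treatment comparison is distorted.* The ratio moves by only about 2% in the cases tried.
- *That the two CSRs would give different rates from the same events.* The final CSR also adds the rest of Safety Follow-up, so events and person-time both change.

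**What to change.** In SAP 2.4.1 and Table 2-2, end AE time at risk at the earliest of:
- last dose + 100 days;
- death;
- end of core-study participation, meaning the later of end of Treatment epoch and end of Safety Follow-up (if entered), with the last documented contact used for patients lost;
- first extension dose;
- analysis cut-off.

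State the cut-off date for the final CSR in SAP 2.1, and have SAP 5.7.2 refer to the new end date. The cost is one derived date and slightly higher reported rates. Addendum 1 shows that a change of this kind is manageable: it replaced the 100-day window for the B-cell depletion summaries after database lock.

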2.4.2 Prior, concomitant and post therapies

Analyses described in this section will be performed on the SAF.

2.4.2.1 Concomitant medication

Records on the Prior and Concomitant Medications CRF page will be coded using the WHO drug dictionary. All medications will be classified as prior, concomitant or post study drug discontinuation medication as follows:

- Prior medications are defined as drugs taken and stopped prior to first dose of study medication.
- Concomitant medications are defined as drugs taken at least once between first dose and last dose of study medication (including those which were started prior to first dose and continued into the treatment period).
- Post-study drug discontinuation medications will be drugs started after the discontinuation of randomized study medication.

Medications will be categorized into one (and only one) of above classes based on recorded or imputed start and end dates. When incomplete or missing, dates will be imputed according to Novartis standards (details will be given in programming datasets specifications (PDS) document). If both start date and end date are completely missing and medication was not

collected on the “Previous MS Disease Modifying Treatment” page, medication will be classified into concomitant medication category.

Medications in each of these 3 categories will be summarized separately by treatment group, ATC code and preferred term. ATC level 1 and level 3 (e.g., M [Musculo-skeletal system], M01A [anti-inflammatory and anti-rheumatic products, non steroids], etc.) will be used.

Data collected from the Previous MS disease modifying treatment pages or as "Injection related premedication" in the concomitant medication pages will not be included in this summary.

2.4.2.2 Surgical and medical procedures

Records on the surgical and medical procedures CRF page will be coded using the MedDRA dictionary. All procedures will be classified as prior, concomitant or post-study drug discontinuation procedure, in the same way as done for concomitant medications. Surgical and medical procedures in each of these 3 categories will be summarized separately by system organ class, preferred term and treatment group.

Imputation rules for start and end dates will follow the same rule as for the concomitant medications.

2.4.2.3 Injection related premedication

Injection related premedication will be identified by subcategory “Injection related premedication” in concomitant medication data set. Injection related premedication will also be summarized separately for each injection up to injection 10 and cumulatively for all injections.

For injection 1 summary, the injection related premedication with either start date or end date on the same day as the first injection date will be included and summarized for each of the three protocol specified types and for each combination of the specified types (type 1+ type 2, type 1+ type 3, type 2+ type 3, type 1+ type 2+ type 3). The three protocol specified types are steroids (type 1), antihistamines (type 2) , and antipyretics/analgesics (type 3) (corresponding to “Acetaminophen” as specified in the table shell for this summary). The steroids (type 1) will be identified by category “Steroid”. The antihistamines (type 2) will be identified by ATC level 3 “antihistamines for systemic use”. The antipyretics/analgesics (type 3) will be identified by ATC level 3 “other analgesics and antipyretics” and “anti-inflammatory and anti-rheumatic products, non-steroids”. In summaries for each combination of the specified types, the number and proportion of patients who took both (or all 3) types of injection related premedication at specified injection will be provided.

Rest injection specific summaries or cumulatively summaries will be reported similarly.

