From Month 2 (5th injection) onwards, patients may inject study medication at home (refer to [Section 5.5.4](#)). Use of premedication is at the discretion of the Investigator. Based on the experience with the initial 4 injections administered at the site and with the use of any premedication, the Investigator will evaluate whether or not premedication (such as acetaminophen and/or antihistamines) should be used before injections administered at home. If premedication is prescribed, the study staff must ensure that the patient will receive a sufficient supply of premedication for home-use (i.e. to last at least until the next visit) and clear instructions (oral and written) about type and dose of premedication, and when to take it (i.e. 30-60 minutes before the injection). The Investigator will evaluate the need for premedication, or a change in the prescription, at each visit (scheduled and unscheduled) including at the monthly telephone interview appointments (interview script includes specific questions about any injection-related symptoms and the use of premedication). If, based on the telephone interview, a change in premedication may be needed, the patient should be asked to return to the site for an unscheduled visit.

The patients must be comprehensively informed (through the patient information and consent process) about the possibility that injection-related reactions may occur despite use of pre-medications and about the possible symptoms of a systemic injection reaction and their management. The patients will additionally receive an injection instructions leaflet (Instructions for Home administration and Use) which also includes information about such reactions, their management as well as Investigator/site contact numbers. Furthermore, patients must be reminded to always carry their Patient Card which includes the Investigator and site telephone contact numbers in case of an emergency.

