May 2019	Prior to DBL	Align with submission planning and update for corrections and clarity	Amendment 2	
Section 2.1: General definition (Updated the CSR name to be consistent with name planned for submission)
 
Section 2.4.1: Time at risk for AE/SAE (Applied the analysis data cutoff date)
 
Section 2.4.2.3: Injection premedication (Updated to include medications either start or end on the injection date for completeness)
 
Sections 2.6.2.1 and 2.6.2.2: Analysis for disability worsening and improvement (Updated model specifications for clarity and accuracy)
 
Section 2.6.2.5: NfL (Added subgroup analysis on brain volume change to align with NfL pre-submission meeting briefing book submitted to FDA on Feb 8th 2019)
 
Section 2.8.1: AEs (Added summary of AEs causing study drug interruptions as required by CSR)
 
Section 2.8.5: Vital signs (minor correction to be consistent with Section 2.1.2.3)
 
Section 2.8.7: Safety data after study drug discontinuation (Clarification that data within 100 days safety cutoff will be included in both “on-treatment” summary as well as in this section)
 

Date	Time point	Reason for update	Outcome for update	Section and title impacted (Current)

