For the first 3 injections, additional summaries will be provided by category of injection related premedication. Specifically, 9 categories are defined as 1) no injection related premedication, 2) type 1, 3) type 2, 4) type 3, 5) type 1+ type 2, 6) type 1+ type 3, 7) type 2+ type 3, 8) type 1+ type 2+ type 3, 9) Any injection related premedication. The types 1 to 3 refer to protocol specified three types of injection related premedication as stated in [Section 2.4.2.3](#).

A separate listing for injection site reaction AEs and injection systemic reaction AEs will be provided where all reported injection related reactions (IRR) (regardless of timing) will be listed along with the corresponding injection sequence number and time to onset from the most recent injection as well as from Day 1. The listing will be sorted by injection of first occurrence of symptoms. Specifically, under the first injection, patients whose first IRR was associated with the first injection will be listed; within a patient all IRRs to all injections will be listed chronologically. Under the second injection, patients whose first IRR was associated with the second injection will be listed; similarly, within a patient all IRRs to all injections will be listed chronologically. The listing will continue with subsequent injections until all patients with IRRs are included in the listing.

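### A multi-day premedication record whose dates strictly span an injection is not linked to that injection, so by-injection premedication use can be undercounted and patients misplaced in the reaction-by-premedication table

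*SAP*

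**What the plan says.** SAP 2.4.2.3 identifies premedication by a subcategory in the concomitant medication data and has it "summarized separately for each injection up to injection 10 and cumulatively for all injections". For injection 1, "the injection related premedication with either start date or end date on the same day as the first injection date will be included". For everything else the section says only: "Rest injection specific summaries or cumulatively summaries will be reported similarly". Neither document adds records that begin before an injection and end after it.

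SAP 2.8.1.1.1 then uses premedication to classify patients: "For the first 3 injections, additional summaries will be provided by category of injection related premedication". The opening of the list is "9 categories are defined as 1) no injection related premedication"; the rest are the three drug types, their combinations, and any premedication. On the types it says "The types 1 to 3 refer to protocol specified three types of injection related premedication as stated in" SAP 2.4.2.3. It gives no linking rule of its own and no separate derivation of the no-premedication category.

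On recording, Protocol 5.5.7 requires every administration of premedication to be entered on the prior and concomitant medications form. It does not require one record per administration. For home injections it asks that the patient receive "a sufficient supply of premedication for home-use (i.e. to last at least until the next visit").

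**The concern.** Whether a patient was premedicated at an injection depends on whether the drug was in use that day. The SAP instead asks whether a record happens to start or stop that day. The two questions have the same answer for single-day records and different answers for longer ones.

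Multi-day records appear to have been expected. If start and end always coincided, naming both dates would be redundant. As context, the SAP's revision history gives the reason for the wording under Amendment 2: "Updated to include medications either start or end on the injection date for completeness". The aim was completeness, and the rule stops short of it.

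Two sets of descriptive output are at stake: the premedication counts for injections 1 to 10, and the summaries of injection reactions by premedication category for injections 1 to 3. There is no backstop in the general medication tables. SAP 2.4.2.1 counts a drug as concomitant if it was started before first dose and continued, but it leaves injection related premedication out of that summary.

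**Working it through.** There is no planned figure to reproduce; the check is date logic.

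**Inputs.** Protocol 3.1 schedules injections on Days 1, 7, 14 and 28, then every 4 weeks. Injections 1 to 10 therefore fall on Days 1, 7, 14, 28, 56, 84, 112, 140, 168 and 196. The example records are illustrative, since neither document shows a completed form.

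**Rules compared.**
- SAP rule: link if start date = injection date or end date = injection date.
- Overlap rule: link if start date ≤ injection date ≤ end date, with an ongoing record treated as open.

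| Record | SAP rule links | Overlap rule links | Not linked by SAP rule |
|---|---|---|---|
| Day 1 only | 1 | 1 | none |
| Day 7 only | 2 | 2 | none |
| Day 1 to 14 | 1, 3 | 1, 2, 3 | 2 |
| Day 1 to 28 | 1, 4 | 1 to 4 | 2, 3 |
| Day 6 to 15 | none | 2, 3 | 2, 3 |
| Day 7 to 28 | 2, 4 | 2, 3, 4 | 3 |
| Day 56 to 140 | 5, 8 | 5 to 8 | 6, 7 |
| Day 56, ongoing, no end date | 5 | 5 to 10 | 6 to 10 |

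Every injection strictly inside a record's date range is missed. Single-day records on the injection date are unaffected. The last row holds only if no end date is imputed; the SAP leaves imputation to a programming specification that is not available here.

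**Effect on use counts.** Let q be the share of truly premedicated patients at an injection for whom no record links. Then reported use ÷ true use = 1 − q. The documents do not give q. Taking assumed values of 0, 10%, 20% and 40%, reported use is 100%, 90%, 80% and 60% of true use.

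**Effect on the injections 1 to 3 table.** Category 1 has no derivation, so it is read as the complement of the linked types. Two cases follow.
- No record links: the patient is placed in the no-premedication category. With a single Day 1 to 28 record this happens at injections 2 and 3.
- Another record links: the patient stays in a premedicated category but in the wrong one. A spanning antihistamine record plus a same-day antipyretic record gives type 3 alone instead of type 2 + type 3.

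**Cumulative summary.** A record with either end on an injection date should still count. Read literally, one that touches no injection date (Day 6 to 15) does not.

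**The case against.** The strongest reply is that the harm is unproven. Protocol 5.5.7 ties premedication to each injection, 30 to 60 minutes beforehand, and requires each administration to be recorded. The natural entry is a record that starts and ends on the injection date, and the SAP rule captures that completely. This stands, and it makes the point conditional on how sites fill in the form. It does not remove it, because the plan does not require single-day entry.

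A reader might take the home-supply text as evidence of misclassification in the reaction table. It is not. It concerns how much drug the patient takes home, and it applies from the fifth injection. The reaction table covers injections 1 to 3, which are given at the site. The text bears at most on use counts for injections 5 to 10.

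A reader might also infer that the table would hide a benefit of premedication. The plan does not support that. It calls for summaries by category with no test and no effect ratio, and premedication is at the investigator's discretion, so the groups are not randomised. Any figure for a diluted effect would rest wholly on assumed risks.

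Finally, overlap linking has its own error: a Day 1 to 28 record does not prove that a dose was taken on Day 7 or Day 14. That is fair, and the fix allows for it. The records concerned are already flagged as injection related, which limits the risk.

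**Conclusion.** The gap is real: as written, the rule does not link a record to an injection lying strictly within its dates, and nothing else in either document does so. If sites enter such records, by-injection use is undercounted, and patients in the injections 1 to 3 table move to the no-premedication category or to the wrong drug combination. The extent cannot be computed; it ranges upward from zero, and zero applies if every administration has its own single-day record. Injection 1 is least exposed, because a premedication record would normally start that day.

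It would go too far to say that premedicated patients will be counted as unpremedicated. That needs multi-day entry and, for the patient concerned, no other linked record. The source data also remain visible, since SAP 2.1 has all data listed. Only descriptive safety tables are touched; the primary, key secondary and overall adverse event analyses are not. Severity is minor, and the correction is a cheap improvement.

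**What to change.** In SAP 2.4.2.3, link a premedication record to an injection when start date ≤ injection date ≤ end date, after the planned date imputation and with records marked ongoing treated as open. State that this applies to every injection and to the cumulative summary. In SAP 2.8.1.1.1, define category 1 as no overlapping premedication record and say that all nine categories use the same link.

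List the patients linked to an injection only through a multi-day or ongoing record, so that a reader can see how far the tables depend on assumed rather than recorded dosing on that day.

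The cost is a few sentences of SAP text, one changed condition in the program and one listing. Every link made by the present rule is kept, and single-day records give identical results. The small downside is that some injections may be credited with premedication that was not taken, which the listing makes visible.
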